12.3.1 Summary Statistics

All summary statistics of continuous variables will include: n, mean, median, standard deviation, minimum and maximum. All summaries presenting frequencies and incidences will include n, % and N, where N is the total number of patients with recorded values in the corresponding group. All confidence intervals will be 2-sided 95% confidence intervals.

Final 5.0 (incorporating Protocol Amendment 4) 06 Jul 2017

Individual patient profiles including information on actual dose will also be presented. For the Dose Escalation part summary statistics will be presented as follows:

- For treatment Cycle 1: by dose cohort and total
- For all treatment cycles: by dose cohort and total
- By indication (all dose cohorts accumulated)

For the Cohort Expansion part, summary statistics will be presented as follows:

- For treatment Cycle 1: by indication and total
- For all treatment cycles: by indication and total

12.4 Statistical Analysis of Primary Endpoint

Incidences of AEs, SAEs, infusion-related AEs, grade \geq 3 AEs, and AEs related to trial drug will be summarized by system organ class and preferred term and listed.

Also, the number of patient days (total number of days in trial) will be shown for each dose group.

12.5 Statistical Analysis of Secondary Endpoints

12.5.1 Clinical Safety Data

Bleeding (major and minor), skin disorders and neuropathy will be summarized and listed separately. Abnormal findings in physical examination, body weight, ECG measurements and vital signs will be listed. Ophthalmological evaluation will be listed.

12.5.2 Laboratory Safety Data

Laboratory assessments (Section 10.16) will be plotted and/or listed for individual patients as appropriate. Laboratory values outside normal range will be listed. Percentage change in laboratory safety parameters from baseline to subsequent visits will be derived and provided in listings. Before and during infusion some laboratory assessments are analyzed locally for monitoring of patient safety.

12.5.3 Response

Response will be assessed in accordance with the RECIST criteria version 1.1 (Eisenhauer et al., 2009), where appropriate. However, specific guidelines may be used (i.e., Rustin et al., 2004 for ovarian cancer and Scher et al., 2008 for prostate cancer).

Final 5.0 (incorporating Protocol Amendment 4) 06 Jul 2017

12.5.3.1 Definition of Response

Table 10: Definition of Response (RECIST Criteria v1.1)

	Category	Criteria		
Based on	Complete	Disappearance of all target lesions. Any pathological lymph no		
target	Response (CR)	must have reduction in short axis to < 10 mm.		
lesions	Partial	\geq 30% decrease in the sum of the LD of target lesions, taking as		
	Response (PR)	reference the baseline sum of LDs.		
	Stable Disease	Neither sufficient shrinkage to qualify for PR nor sufficient		
	(SD)	increase to qualify for PD, taking as reference the smallest sum of		
		LDs while in trial.		
	Progressive	\geq 20% (and \geq 5 mm) increase in the sum of the LDs of target		
	Disease (PD)	lesions, taking as reference the smallest sum of the target LDs		
		recorded while in trial or the appearance of 1 or more new lesions.		
Based on	CR	Disappearance of all non-target lesions and normalization of tumor		
non-target		marker level. All lymph nodes must be non-pathological in size		
lesions		(< 10 mm short axis).		
	SD	Persistence of 1 or more non-target lesion(s) or/and maintenance		
		of tumor marker level above the normal limits.		
	PD	Appearance of 1 or more new lesions and/or unequivocal		
		progression of existing non-target lesions.		

LD=Longest Diameter

Response will be evaluated after four cycles (16 weeks) and as best overall response. The best overall response is the best response recorded from the start of the treatment until disease progression (Table 11).

Table 11: Evaluation of Response

Target Lesions	Non-target Lesions	New Lesions	Response
CR	CR	No	CR
CR	SD or PR	No	PR
PR	Non-PD	No	PR
SD	Non-PD	No	SD
PD	Any	Yes or No	PD
Any	PD	Yes or No	PD
Any	Any	Yes	PD

CR=Complete Response; PD=Progressive Disease; PR=Partial Response; SD=Stable Disease

For patients with CRPC, when the bone scan is the sole indicator of progression, PD is defined in bone when at least ≥ 2 new lesions are seen on the bone scan compared with a prior scan for trial entry. There are no validated criteria for response on radionuclide bone scan. For

Final 5.0 (incorporating Protocol Amendment 4) 06 Jul 2017

control/relief/eliminate endpoints, it is recommended that post-treatment changes are recorded as either "no new lesions" or "new lesions." However, PD at the first scheduled assessment should be confirmed on a second scan performed six or more weeks later, in the absence of clearly worsening soft-tissue (nodal and visceral) disease or disease-related symptoms. In case where visible lesions disappear, this should be confirmed at the next scheduled assessment too.

For patients with ovarian and endometrial cancer, a response according to CA 125 has occurred if there is at least a 50% reduction in CA 125 levels from a pretreatment sample. The response must be confirmed and maintained for at least 28 days. Patients can be evaluated according to CA 125 only if they have a pretreatment sample that is at least two × ULN and within two weeks prior to starting treatment.

Evaluation of best overall response

The best overall response is the best response recorded from the start of the treatment until disease progression/recurrence (taking as reference for PD the smallest measurements recorded since the treatment started).

Patients with a global deterioration of health status requiring discontinuation of treatment without objective evidence of PD at that time should be classified as having "symptomatic deterioration". Every effort should be made to document the objective progression even after discontinuation of treatment.

Confirmation

SD: follow-up measurements must have met the SD criteria at least once and for a minimum time period of six weeks (\pm 7 days) after first treatment.

PR and CR: no formal confirmation response is required. However, a repeat CT-scan will be performed no less than four weeks (± 7 days) after the criteria for response is met to substantiate/confirm CT response (Section 10.7).

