 - Endometrial cancer: failing platinum-based therapy. Patients must have received no more than four prior treatment regimens for advanced disease (excluding adjuvant chemotherapy).
 - Esophageal cancer (esophageal cancer or gastro-esophageal junction cancer): failing platinum-based therapy with or without taxanes depending on established SoC therapy. Patients must have received no more than three prior treatment regimens for advanced disease.
 - o NSCLC: failing at least one platinum-based regimen. Patients with epidermal growth factor receptor (EGFR) or anaplastic lymphoma kinase mutations should have been treated with appropriate targeted therapy before trial entry. Patients must have received no more than four (five allowed for patients with EGFR mutated adenocarcinomas) prior treatment regimens for advanced disease.

Other inclusion criteria:

- 2. Patients must have measurable disease according to RECIST (Response Evaluation Criteria In Solid Tumors) version 1.1 (Eisenhauer et al., 2009).
 - o A minimum of one lesion ≥ 10 mm in the longest diameter (LD) from a non-irradiated area. If target lesion(s) are located within previously irradiated area

Final 5.0 (incorporating Protocol Amendment 4)

only, the patient can be enrolled only if there has been demonstrated progression in the "in field" lesion and after sponsor acceptance.

- Lymph nodes lesion ≥ 15 mm in the shortest diameter from a non-irradiated area.
- Patients with prostate cancer must be clinically refractory and resistant to hormone therapy as documented by progression (CRPC) and can be included based on PSA and/or bone metastases according to the Prostate Cancer Working Group Guideline (Scher et al., 2008).
- Patients with ovarian cancer can be included based on CA 125 positivity according to the Gynaecologic Cancer Intergroup Guideline (Rustin et al., 2004). This is only applicable for the Dose Escalation part of the trial.
- 3. Age \geq 18 years.
- 4. Acceptable renal function defined as:
 - o Glomerular filtration rate (Cockroft-Gault) > 45 mL/min.
- 5. Acceptable liver function defined as:
 - Alanine aminotransferase (ALT) and aspartate aminotransferase (AST) ≤ 3 times the upper limit of normal (ULN); if liver tumor/metastases are present, then < 5 × ULN is allowed.
 - o Bilirubin \leq 1.5 × ULN, except in patients diagnosed with Gilbert's syndrome, direct bilirubin \leq 2 × ULN.

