12.5.3.2 Response Evaluation and Reporting of Results

Response evaluation will be performed by external medical experts in relevant cancer types in collaboration with the sponsor Medical Officer and a Statistician.

Each patient will be assigned one of the following categories:

- 1) CR
- 2) PR
- 3) SD
- 4) PD or
- 5) Not Evaluable

Patients in response categories 1 and 2 are considered responders and patients in response categories 4 and 5 are considered as failing to respond to treatment (disease progression). Patients in response categories 1, 2 and 3 are considered to be in disease control.

Final 5.0 (incorporating Protocol Amendment 4)

Individual patient data listings and summaries of objective response, best overall tumor response and disease control will be presented by dose cohort and total. For respective patients, PSA (CRPC) and CA125 (ovarian and endometrial) will be listed.

The maximal response (maximal change in the sum of the LD in the target lesions) in target lesions at any time on trial will be reported using waterfall plots.

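### PR, SD, PD and the waterfall plot use longest diameters for every target lesion, although nodes are selected and cleared by short axis; this can misclassify patients with nodal target lesions

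*Protocol*

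**What the plan says.** **Entry (Section 8.3.1, criterion 2).** Two axes are kept apart. A general lesion qualifies at 10 mm or more "in the longest diameter (LD) from a non-irradiated" area. A lymph node qualifies at 15 mm or more "in the shortest diameter from a non-irradiated area".

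**Complete response (Section 12.5.3.1, Table 10).** A pathological node "must have reduction in short axis to < 10 mm". The row for non-target lesions applies the same 10 mm short-axis limit.

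**Partial response, stable disease and progression (same table).** PR needs a 30% "decrease in the sum of the LD of target lesions, taking as" reference the baseline sum. PD needs a 20% (and at least 5 mm) "increase in the sum of the LDs of target" lesions, measured from the smallest sum on trial. SD is whatever meets neither rule. The table note reads "LD=Longest Diameter", and no row makes an exception for nodes.

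**Waterfall plot (Section 12.5.3.2).** The plotted quantity is the "maximal change in the sum of the LD in the target lesions".

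**Scan reading (Section 10.7).** Up to five target lesions, at most two per organ, are chosen at screening. No measuring axis is named for nodes.

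**The concern.** A node is admitted and cleared on one dimension, then scored for shrinkage and growth on another. The two dimensions need not change in the same proportion. They also give the node a different weight in the sum when other target lesions are present. A patient with nodal target disease can therefore fall on either side of the 30% or 20% cut-off depending on the axis.

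Objective response, disease control, PFS, DoR and tumor shrinkage all draw on these rules. The expansion part has 20 to 30 patients in two or three arms (Section 12.9). If the arms are equal, that is between 20/3 = 6.7 and 30/2 = 15 patients per arm. One patient crossing the PR line then moves an arm's response rate by 100/15 = 6.7 to 100/6.7 = 15 percentage points.

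**Working it through.** The protocol gives no figure to reproduce here: no test or power calculation bears on a definition. The check applies Table 10's own cut-offs to example lesions in two ways.

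**Inputs from the protocol.** PR: fall of at least 30% from baseline. PD: rise of at least 20% and at least 5 mm from the smallest sum. Node entry: short axis at least 15 mm. Nodal CR: short axis below 10 mm.

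**Assumed inputs.** All lesion sizes. Baseline is taken as the smallest sum for PD, with no new lesion and no non-target progression.

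**Formula.** Change = (sum now / reference sum) - 1. Method A adds the longest diameter of every target lesion, as written. Method B adds the longest diameter of non-nodal lesions and the short axis of nodes. Nodes are shown as short x long, in mm.

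| Case | A: longest diameters, as written | B: short axis for nodes |
|---|---|---|
| 1. Node 18x30 to 12x24 | 30 to 24, -20%: SD | 18 to 12, -33.3%: PR |
| 2. Lesion 20 + node 16x30 to lesion 15 + node 9x24 | 50 to 39, -22%: SD | 36 to 24, -33.3%: PR |
| 3. Node 20x40 to 26x44 | 40 to 44, +10%: SD | 20 to 26, +30% and +6 mm: PD |
| 4. Lesion 10 + node 18x35 to lesion 10 + node 24x38 | 45 to 48, +6.7%: SD | 28 to 34, +21.4% and +6 mm: PD |
| 5. Node 20x28 to 21x35 | 28 to 35, +25% and +7 mm: PD | 20 to 21, +5%: SD |
| 6. Node 16x30 to 14x20 | 30 to 20, -33.3%: PR | 16 to 14, -12.5%: SD |

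In cases 1 to 4 the longest-diameter rule misses a PR or PD that the short-axis rule would call. Cases 5 and 6 run the other way. In case 2 the node falls below 10 mm, but the other target lesion persists, so the CR row does not apply and the sum decides.

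**Waterfall plot.** Take a sole target node going from 15x25 to 9x20. It meets the nodal CR limit. The plotted change is 20/25 - 1 = -20%, short of the -30% line. On the short axis it is 9/15 - 1 = -40%. More generally, a node that was at least 15 mm at baseline and is below 10 mm has lost more than 1 - 10/15 = 33.3% of its short axis, so on that axis a nodal complete responder always lies beyond -30%. Longest diameter gives no such guarantee.

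**How often categories might differ.** An illustrative simulation assumed one target node (short axis 15 to 30 mm, long/short ratio 1.2 to 2.0) with independent variation of the two axes of 10 to 20% on the log scale. The two methods disagreed in about 19 to 35% of patients with nodal target disease only, 10 to 20% with one added non-nodal lesion, and 6 to 11% with three. Overall PR and PD rates moved by 2 points or less, because the differences ran both ways. The simulation did not apply the CR row first, so the nodal-only figure includes some patients whom that row would settle. These figures describe the assumptions, not this trial.

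**The case against.** **The cited standard governs.** Section 12.5.3 says response follows RECIST 1.1, Table 10 carries that label, and Section 12.5.3.2 has external medical experts assign the categories with the sponsor Medical Officer and a statistician. LD may be loose shorthand, and practice may already use the short axis for nodes. That may be so. But the citation is qualified as applying where appropriate, nothing says it overrides the table, and the table spells out its own rule. One reader following the table and another following the citation could measure differently.

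**A sole target node raises no conflict.** A reader might infer that a node going from 16x28 to 9x22 is at once CR and SD. The documents do not support that. If it is the only target lesion, the CR row is met, and SD is the residual category. A conflict of category needs a node that stays at 10 mm or more, or another target lesion that persists. What remains for the sole node is the misleading waterfall bar.

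**An entry axis need not be the response axis.** This stands as logic. The protocol's text shows mixed axes; it does not by itself prove that short axis is right for the PR and PD sums. The case for short axis here is consistency with the protocol's own entry and CR rules.

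**The stakes are limited.** Also true. The primary endpoint is adverse events, and no formal tests are planned. PD can also arise from new lesions or non-target progression, and PFS and DoR also end at death.

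**The SAP can settle it.** Section 12.1 has the SAP expand on protocol detail. This point was not left open, though: the protocol states a rule, and the axis must be fixed when scans are read.

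**Conclusion.** The point holds as an internal inconsistency that can change PR, SD or PD for individual patients with nodal target lesions, in either direction, and can move PD dates. It arises only when a target node's two axes change in different proportions, or when the node's weight in the sum matters. Patients without target nodes are unaffected.

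A reader might infer that nodal disease is generally misclassified, or that response rates are biased one way. Neither is supported. The protocol does not give the share of patients with target nodes, the examples rest on assumed sizes, and the differences run both ways. The effect is confined to secondary endpoints. It is worth correcting because arms are small and the correction is simple, but it does not threaten the primary safety assessment.

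**What to change.** In the PR, SD and PD rows of Table 10, and in the waterfall sentence of Section 12.5.3.2, replace the sum of longest diameters with: *sum of diameters (longest diameter for non-nodal, short axis for nodal target lesions)*. In Section 10.7, state that nodal target lesions are measured by short axis at baseline and at every later scan. Check the final wording against the cited RECIST 1.1 text.

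The document change is a few lines. The possible further cost is re-reading: this is version 5.0 and expansion patients have already been dosed. If sites recorded only longest diameters for target nodes at follow-up, the short axes must be taken from existing scans. If readers already used the short axis, the change only brings the text into line with practice.

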10.7 Computerized Tomography

All patients will have a CT-scan with contrast of thorax, abdomen and pelvis performed during screening. If there is suggestion of brain metastases/tumors, a CT-scan of the head will be performed before inclusion.

Up to five target lesions (maximum two per organ) will be defined at screening and these must be followed throughout the trial. Non-target lesions will also be assessed throughout the trial.

Final 5.0 (incorporating Protocol Amendment 4) 06 Jul 2017

Scans will be repeated every six weeks (at the end of every second cycle) during the trial period. If the result is PR or better, CT-scan should be repeated after four weeks to confirm response. CT-scans can be performed up to seven days before Day 1 of the relevant cycle to ensure results are available before subsequent dosing.

Additional CT-scans may be performed at the investigators' discretion to confirm response or new symptoms. In this case, the investigator must choose the imaging technology based on the clinical indication.

Magnetic resonance imaging can be performed instead of a CT-scan if the patient is allergic to iodine contrast or at the discretion of the investigator, after approval of the sponsor.

The reading of the surveys will be done by a radiologist. Sites should attempt to maintain the same radiologist throughout the trial. The overall interpretation of the evaluation shall be recorded in the eCRF and a copy of the evaluation reports should be kept in the patient's file.

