12.3 Statistical Methods

The presentations will be done separately for the Dose Escalation part and the Cohort Expansion part.

In the reporting of the Dose Escalation part tables will report by cohort, while in the Cohort Expansion part tables will report by indication.

The shift from the 3q4wk dosing to the once q3wk dosing in the Cohort Expansion part may lead to a need for reporting some tables by dosing schedule. This will be described as appropriate in the SAP.

No formal statistical tests will be performed.

For efficacy analyses, the quartile estimates of PFS and DoR from the Kaplan-Meier product limit algorithm will be presented (Kaplan and Meier, 1958). The 2-sided 95% confidence interval will be presented as well. The number of events may be small, and thereby limit use of the Kaplan-Meier method to provide reliable information. In this case, descriptive statistics (e.g., n, mean, standard deviation, median, minimum and maximum) for PFS or DoR will be presented. Objective response (CR or PR) rate will be determined along with the corresponding 2-sided 95% exact binomial confidence interval.

All data will be listed. Baseline is defined as the latest available measurement made before the first treatment with tisotumab vedotin (HuMax-TF-ADC).

A patient will be considered as having completed the trial when all planned trial visits have been performed.

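### A single scan decides objective response and starts DoR, although a repeat CT to confirm response is already planned and has no stated role

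*Protocol*

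**What the plan says.** Protocol Section 12.5.3.1 fixes the rule for CT-based response: "PR and CR: no formal confirmation response is required". Its next sentence adds that "a repeat CT-scan will be performed no less than four weeks" (± 7 days) after the response criteria are met, for the purpose of substantiating the response. Section 10.7 asks for the same scan: "If the result is PR or better, CT-scan should be repeated after four weeks to confirm response".

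The remaining definitions carry a single reading through to the endpoints:

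- Section 12.5.3.1: "The best overall response is the best response recorded from the start of the treatment until disease progression".
- Section 12.5.3.2: "Patients in response categories 1 and 2 are considered responders", these categories being CR and PR.
- Section 12.5.3.4: DoR runs from the first documented CR or PR.
- Section 12.3: "Objective response (CR or PR) rate will be determined along with the corresponding 2-sided 95% exact binomial confidence interval".

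Other favourable outcomes in Section 12.5.3.1 are held to more. For a CA 125 response, "The response must be confirmed and maintained for at least 28 days". Disappearance of visible bone lesions should be confirmed at the next scheduled assessment. SD must hold for a minimum of six weeks.

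**The concern.** The protocol plans a scan whose purpose is confirmation and then gives its result no place in the response definition. A patient with PR on one CT whose repeat CT no longer meets the criterion remains a responder and has a DoR start date.

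Best overall response takes the most favourable of several measurements, each with error. One low reading is enough, and later readings cannot undo it. In an open-label trial without a control arm, nothing else in the analysis offsets that. The Cohort Expansion part is meant to give preliminary efficacy data and is reported by indication, so a single doubtful responder can visibly move the rate in a small arm.

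**Working it through.** **No figure to reproduce.** The protocol states no target ORR, power, precision or measurement error. The direction follows from the definitions. The size rests on assumptions.

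**Inputs from the protocol.**

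- PR threshold: a decrease of at least 30% from the baseline sum of diameters (Table 10).
- Scheduled post-baseline CTs in the Cohort Expansion part: Day 1 of Cycles 3, 5, 7 and 9, so four, plus one at EOT (Table 5, footnote 12).
- Size of the Cohort Expansion part: 20 to 30 patients in two or three arms (Sections 8.3 and 12.9).

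**Direction.** Every confirmed responder is also a single-scan responder, so single-scan ORR ≥ confirmed ORR in any data set. With random error the difference is positive in expectation.

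**Simple bound with independent errors.** Let q be the assumed chance that a non-responder reads as PR on one scan. Over four scans the chance of being counted is 1 − (1 − q)^4 unconfirmed. If each such reading needs one independent repeat, it is 1 − (1 − q²)^4.

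| q | unconfirmed | confirmed |
|---|---|---|
| 1% | 3.9% | 0.04% |
| 2% | 7.8% | 0.16% |
| 5% | 18.5% | 1.0% |

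This overstates the contrast, because all of a patient's percentage changes share one baseline measurement.

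**Simulation with shared baseline error.** Measured ratio at scan j = (1 + δ)·exp(ε_j)/exp(ε_0), where δ is the true change, ε_0 is one baseline error per patient, and every ε is normal with SD s on the log scale. PR means a ratio ≤ 0.70. Confirmed means that the scan and its own repeat are both ≤ 0.70. There were 400,000 patients per setting, each with four scans and a constant δ.

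For a borderline patient with true shrinkage of 20%, the chance of being called PR is 9.1% unconfirmed against 1.8% confirmed at s = 5%, and 39.7% against 17.6% at s = 10%.

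For the trial-level effect, an assumed mix was used: true change +10% in 30% of patients, 0 in 20%, −10% in 20%, −20% in 15% and −45% in 15%. The last group are the true responders.

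| s | single-scan ORR | confirmed ORR | excess (points) | excess per 30 patients |
|---|---|---|---|---|
| 5% | 16.4% | 15.2% | 1.1 | 0.3 |
| 8% | 20.4% | 16.8% | 3.6 | 1.1 |
| 10% | 23.7% | 18.0% | 5.7 | 1.7 |

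Excesses are taken from unrounded rates. With only two scans per patient, as after early progression, they fall to 0.6, 2.4 and 3.9 points.

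**Scale.** With N = 30, 5 responders give 16.7% (exact 95% CI 5.6 to 34.7%) and 7 give 23.3% (9.9 to 42.3%). An even split gives arms of about 7 (20/3) to 15 (30/2), where one responder moves the rate by about 14 (1/7) to 7 (1/15) points.

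**Availability of the repeat CT.** On the 21-day schedule, Cycle 9 Day 1 falls after 8 × 3 = 24 weeks, so a repeat four weeks later falls at about week 28. Section 8.1 puts nine cycles at about 27 weeks. Section 8.1.1.4 provides no follow-up visits in the Cohort Expansion part, and Section 8.1.1.5 times the EOT visit there only for PD, new treatment or withdrawal. A response first seen at Cycle 9 may therefore have no scheduled visit for its repeat.

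**The case against.** The best case for leaving the plan alone has four parts.

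- **It may belong in the SAP.** Section 12.1 says the SAP will expand on the protocol and may add analyses. It was not at hand, and a confirmed-response table may already be planned. That stands as a caution. It does not remove the point, because the protocol states a rule here instead of leaving a gap.
- **The rule is deliberate.** A reader might infer that the protocol contradicts itself or discards the repeat scan. It does neither. Not requiring confirmation while still taking the scan is coherent. Section 12.3 promises that all data will be listed, and Section 12.5.3.2 has external experts evaluate response. What is missing is any consequence when the repeat disagrees. Expert review may reduce reading error but adds no confirmation step. The CA 125 contrast is context, not proof, since different measures may have different rules.
- **Nothing is decided on ORR.** It is secondary, and "No formal statistical tests will be performed". This stands: type I error and sample size are untouched.
- **Confirmation has its own errors.** It does not remove baseline error: the simulated confirmed rate still exceeds the assumed 15%. It also loses true responders near the threshold. At a true shrinkage of 35%, s = 10% and four scans, 92.8% are counted unconfirmed and 81.3% confirmed. Late responders without a repeat CT could be lost as well. This stands, and is why both rates should be shown.

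**Conclusion.** The point holds as a modest improvement to reporting. The stated rule lets a response that the planned repeat CT does not bear out count in ORR and start DoR, and it makes ORR at least as high as the confirmed rate. Under the assumptions set out above, the excess is about 1 to 6 percentage points, or 0.3 to 1.7 responders in 30. That is small beside an exact interval about 29 points wide at 5 of 30.

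A reader might infer a much larger effect from borderline patients alone. With independent errors of SD 8 to 10 points, a patient with a true 20% shrinkage has a per-scan chance of 10.6 to 15.9% of reading as PR. By the formulas above, that gives 36 to 50% over four scans unconfirmed, against 4 to 10% confirmed. Those figures describe patients placed near the threshold, not the trial's ORR, and they ignore the shared baseline. Nor do the documents support attributing the whole gap to measurement error, since some may be real but brief shrinkage. The effect on DoR has no certain direction.

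**What to change.** Keep the unconfirmed analysis and add, in the protocol or the SAP:

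1. Confirmed ORR with its exact two-sided 95% CI, beside the unconfirmed ORR. Confirmed means that CR or PR is met again on the repeat CT of Sections 10.7 and 12.5.3.1, with the allowed window stated once.
2. DoR in confirmed responders, beside DoR in all responders.
3. A split of single-scan responders into confirmed, not confirmed on repeat, and no repeat CT available. Patients in the last group, such as those first responding at Cycle 9 with no later scheduled visit, should be counted as such and not silently treated as non-responders.
4. Statements on anti-tumour activity that show both rates.

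The cost is a few table rows and no newly required scans. The downside is that the confirmed ORR may look less favourable and may miss some late responders.
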